Participant Recruitment, Baseline Survey Administration, and Randomization. Initially, Hispanic patients who are 50 to 75 years of age, have not been diagnosed with CRC, and have not had a recent CRC screening test will be identified via LVHN electronic records. These individuals will be mailed a study invitation letter in English and Spanish. The letter will describe the proposed research and provide information about ways to opt out of or register to participate in the study (i.e., complete and return a study registration card in an addressed postage-paid return envelope, or call a toll-free telephone number.) The letter will also inform recipients that a research staff member will call non-respondents.

A trained bilingual research assistant will call patients within 15 days after the invitation letter mailing. The research assistant will conduct the call in the language preferred by the respondent. The research assistant will verify patient eligibility, describe the study, ascertain patient willingness to participate, obtain verbal consent, and administer a brief baseline survey to a total

of 400 participants. As part of the survey, the research assistant will describe SBT and colonoscopy screening, and will ascertain the participant’s overall and test-specific screening decision stage. We will use this information to determine the participant’s overall CRC screening decision stage and preferred CRC screening test. Data on sociodemographic background will also be collected. At the end of the baseline survey, the interviewer will ask participants to indicate a day(s) of the week and time(s) of the day when research staff can most conveniently speak to the participant by telephone. The interviewer will also ask for a telephone number and email address for use in making contact. Finally, the research assistant will inform the participants that they will receive CRC screening materials in the mail, will determine whether the participant wants to receive study materials in English or Spanish, and will mention that the research team may contact them by telephone to discuss screening and will contact them to complete two follow-up surveys. As shown in **Figure 1**, research staff will randomly assign all consented participants either to a SI Group or a DSNI Group. Random assignment will be stratified by participant primary care practice.

Figure 1. Study Design					

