Baseline Survey	Randomization	Intervention Delivery		Records Review (6,12 month)	6-Month Survey
Complete (N = 400)	Stratify random assignment by primary practice	Standard Intervention (SI) (n = 200)	Mailed contacts*	Complete (n = 190)	Complete (n = 160)
		Decision Support and Navigation Intervention (DSNI) (n = 200)	Mailed contacts, Support/Navigation contacts**	Complete (n = 190)	Complete (n = 160)
* Mailed Contacts: Screening letter, informational booklet, colonoscopy instructions, SBT kit, and reminder letter.					
**Mailed Contacts: Screening letter, informational booklet, colonoscopy instructions, SBT kit, and reminder letter; Support/Navigation contacts: navigator calls to provide decision counseling, develop screening plans, support plan implementation, and deliver screening plan and status reports.					

Intervention Implementation. Following randomization, **SI Group** participants will be mailed a set of standard materials. The materials will include a letter from the participant’s primary care practice encouraging selection and performance of either (1) colonoscopy screening, or (2) stool blood test (SBT). Accompanying the letter will be instructions for arranging a colonoscopy appointment and instructions for completing an enclosed immunochemical SBT kit. Print materials and contacts will be provided in the language the participant as preferred (English or Spanish) at the time of the baseline survey. At 45 days following random assignment, research staff will send participants a reminder letter from the participant’s primary care provider that endorses and encourages screening. Study participants assigned to the **DSNI Group** will also be

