Both focus groups will be audio recorded and will be transcribed prior to initiating the coding process. Fox Chase Cancer Center OHCHD staff will develop a coding scheme using MaxQDA professional text analysis and content analysis software; and will review data output to identify the most common themes and responses voiced by participants. Basic descriptive statistics (frequencies) will reveal key themes, which will be presented in a formal report.

Patient and Stakeholder Advisory Committee Meetings

The initial meeting and all subsequent meetings of the PASAC will be audio recorded. OHCHD staff will transcribe and analyze the audio recordings to create an objective record of PASAC meeting discussions, recommendations made by participants, and research team responses to those recommendations. This level of reporting is likely to improve balanced participation, ensure that the patient voice is represented in study operations, and contribute to the patient-centeredness of the study.

Research Study Procedures

The study will rely on a randomized design to assess the two interventions. Because of this design, we expect the two intervention groups to be comparable with respect to all participant and practice characteristics. However, if there is substantial imbalance in any of the baseline variables, the analyses will control for them. Some of the planned analyses will rely solely on endpoint survey data (Aims 2 and 4) and survey non-response might negatively impact study group comparability. In our prior research, we have found that overall non-response rates and the characteristics of non-respondents (i.e., non-response patterns) do not differ substantially across different types of CRC screening interventions, suggesting little missing data bias. Nevertheless, we plan to control for all baseline characteristics to account for any differential missing data patterns. In addition, we will also explore multiple imputation analyses, particularly if the endpoint survey non-response is higher than expected. Research data will be described for each study group using both graphical methods (boxplots for continuous variables, and bar graphs for categorical variables) and summary statistics (mean and standard deviation for continuous variables, frequency counts and percentages for categorical variables). Main analyses will follow the intent-to-treat principle and will control for practice (stratification variable at randomization).

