Aim 1 (DSNI versus SI on overall CRC screening adherence). The two study groups will be compared in terms of the fraction of participants who undergo CRC screening (through SBT, colonoscopy, flexible sigmoidoscopy, etc.) within 12 months of the randomization date. Screening status will be determined using both the 6-month survey and 12-month medical records review data. We hypothesize that DSNI Group participants will have higher overall screening than SI Group participants. We will analyze screening (yes vs. no) via logistic regression, using study group (DSNI versus SI) as the main predictor. As mentioned above, we expect the two study groups to be comparable at baseline due to randomization. So, the model will control only for practice and participant gender and age (the latter two variables will be included to allow addition of interaction between study group and gender or age in secondary analyses). If, however, substantial baseline imbalances occur, the model will include for those additional variables.

Aim 2 (DSNI versus SI on change in CRC screening decision stage). CRC screening decision stage will be assessed in both the baseline and 6-month surveys. Forward change (between baseline and endpoint) will encompass any movement from a lower to a higher decision stage. We hypothesize that DSNI Group participants will have greater forward movement in screening decision stage than SI Group participants. We will analyze forward change in screening decision stage (yes vs. no) via logistic regression. These analyses will be based on 6-month survey data. Prior research suggests that survey response will be comparable in both study groups. The model will include practice and participant baseline characteristics.

Aim 3 (DSNI versus SI on test-specific CRC screening adherence). The two study groups will be compared in terms of the fraction of participants who undergo a SBT or a colonoscopy within 12 months. Due to current screening practices in primary care, we expect very few, if any, instances of screening via other modalities. We hypothesize that DSNI Group participants will have higher SBT and colonoscopy screening than SI Group participants. The main analysis of test-specific screening (no screening, SBT screening, colonoscopy screening) will be based on polytomous (multinomial) logistic regression. The analysis strategy will be similar to that for Aim 1 (i.e., control for practice, as well as participant gender and age).

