The PASAC committee will review surveys so that the questions are relevant to patients. In addition, data will be double-entered and verified in the database in order to assure accuracy. Finally, all analyses will be done by or with the assistance of biostatisticians so that results and conclusions are accurate.

7. Identify the sources of data obtained about human subjects in the form of specimens, records, survey instruments, interviews, focus groups, observation, or other sources.

Data Type	Data Elements	Data Source
Demographic data	Name, telephone number(s), mailing address, insurance status	LVHN IDX administrative database
Demographic data	Age, ethnicity, race, education, income and marital status. E-mail address and cell telephone number. Language preference.	Baseline survey
Medical Records data	Colorectal cancer related screening and diagnostic history	LVHN IDX administrative database
Data collected for the study	Decision stage related to screening SBT and colonoscopy	Baseline & 6-month survey
	Decision factors, factor weights, screening likelihood score	Decision counseling session (DSNI Group only)
	Factors that influence screening, barriers to screen and steps in the screening plan.	Navigation log
	SBT (FIT or some other SBT) and colonoscopy screening use. Flexible sigmoidoscopy and barium enema x-ray use. Test-specific decision stage, acculturation, fatalism, and perceptions regarding CRC screening and CRC screening knowledge	6-month survey
	SBT(FIT or some other SBT) and colonoscopy Screening use. Flexible sigmoidoscopy and barium enema x-ray use.	6- and 12-month medical records review/EMR

8. Please check off those steps noted below that you intend to implement to ensure confidentiality of Subject data and to protect the identifiers or codes that can be linked to identifiers from improper use or disclosure. (Note: Non-Jefferson sanctioned “covered devices” may **not** be used for the storage of identifiable Subject data. See **Jefferson Policy #122.35, “Wireless and Portable Device Security Policy.”**)

- List of identifiers will be kept in a separate location from the coded Subject data that can be linked to identifiers.
- Subject data will be kept in a locked filing cabinet or desk and in a locked office.
- Subject data will be kept on a password-protected, encrypted on-site computer.
- Subject data will be kept on a Jefferson server. Provide specific physical and/or electronic location:

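### Aim 1 primary model: pre-specify baseline decision stage, and keep imbalance-triggered covariates for a sensitivity analysis

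*Combined protocol and SAP*

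**What the plan says.** The Aim 1 paragraph of Part A, 4c specifies a logistic regression of screening (yes/no) on study group: "So, the model will control only for practice and participant gender and age". Practice is the stratification factor. Gender and age are not there as predictors of screening: "the latter two variables will be included to allow addition of interaction between study group and gender or age".

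Other covariates enter conditionally: "If, however, substantial baseline imbalances occur, the model will include for those additional variables". The general analysis text in the same section has the same rule: "if there is substantial imbalance in any of the baseline variables, the analyses will control for them". Neither place gives a threshold, a list of variables or a coding.

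Part A, 4b says the baseline survey will be used to determine the participant's "overall CRC screening decision stage and preferred CRC screening test". Figure 1 places that survey before randomization and shows it complete for all 400. The data-source table in Part A, item 7 lists further baseline variables, including "Age, ethnicity, race, education, income and marital status", language preference and insurance status.

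Aims 2 and 4 adjust more fully, for a separate reason, survey non-response: "we plan to control for all baseline characteristics to account for any differential missing data patterns". That difference from Aim 1 is not an inconsistency.

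**The concern.** There are two separate points.

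**Power.** In a logistic model, adjusting for a baseline variable that predicts the outcome raises the power of the treatment test whether or not the arms happen to be imbalanced on it. A rule that adjusts only after imbalance therefore collects only part of the available gain. Decision stage is an obvious candidate. It is measured before randomization, and Aim 2 already needs it in ordered form. If it predicts screening, the plan gives up power on its first primary objective that would need no new data.

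**A fixed primary model.** While the imbalance clause applies to the primary analysis, the covariates behind the primary odds ratio are settled only after baseline data are seen, by a judgement with no stated criterion. Adding stage alone would not cure this, because the clause covers every baseline variable.

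Neither point makes the planned analysis biased, and no inflation of type I error is claimed.

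**Working it through.** **1. The plan's own figure.** Inputs from Power for Aim 1 (Part A, 4c): 30% versus 45%, N = 380 (190 per arm), two-sided alpha 0.05. With a pooled variance under the null:

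z = [0.15·√190 − 1.96·√(2·0.375·0.625)] / √(0.30·0.70 + 0.45·0.55) = (2.068 − 1.342) / 0.676 = 1.073

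Power = Φ(1.073) = 85.8%. The odds ratio is (0.45/0.55)/(0.30/0.70) = 1.91. The stated 85% and 1.9 reproduce.

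**2. Power with and without stage.** The documents give no stage categories, distribution or association with screening, so these are assumed and varied. There were 12,000 simulated trials per scenario, with 190 per arm and 5 practices. Practice, gender and age were in every model, and group was tested by Wald at |z| > 1.96. The base case has three stages (35/35/30%), with marginal rates held at 30% and 45%. Power (%) under a common conditional odds ratio:

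| OR per SD of stage | SI rates by stage (%) | Planned model | Adjust if std. diff. > 0.10 | Adjust if > 0.20 | Always adjust |
|---|---|---|---|---|---|
| 1.47 | 21/30/41 | 86.4 | 86.7 | 86.5 | 87.2 |
| 2.0 | 15/29/49 | 85.8 | 87.6 | 86.4 | 89.0 |
| 2.38 | 12/28/53 | 86.2 | 88.8 | 86.9 | 90.9 |
| 3.15 | 8/26/60 | 85.9 | 89.5 | 86.9 | 93.3 |

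Share of the gain recovered by the > 0.10 trigger: 1.8/3.2 = 56%, 2.6/4.7 = 55% and 3.6/7.4 = 49% at OR 2.0, 2.38 and 3.15. For the > 0.20 trigger: 0.6/3.2 = 19%, 0.7/4.7 = 15% and 1.0/7.4 = 14%.

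**3. Sensitivity of the gain to the form of the effect.** Gain in power points from always adjusting (Monte Carlo 95% limits ±0.2 to 0.5; rounding explains 0.1-point differences from the table above):

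| Form of treatment effect | OR 1.47 | 1.75 | 2.0 | 2.38 | 3.15 |
|---|---|---|---|---|---|
| Common odds ratio | +0.7 | +2.3 | +3.2 | +4.7 | +7.3 |
| Constant risk difference | +0.8 | +1.8 | +2.7 | +4.2 | +6.6 |
| No effect in the top stage | +0.2 | +1.3 | +1.6 | +2.4 | +5.0 |

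With no link between stage and screening, the change was −0.1 (three stages), +0.1 (skewed, 70/20/10%) and −0.1 (four stages). At OR 2.0 the skewed and four-stage structures gave +3.8 and +3.0. With age correlated 0.5 with stage, the gains at OR 2.38 and 3.15 were +3.8 and +6.0.

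A separate simulation used stages of 25/50/25%, 6,000 trials per scenario and no other covariates in either model. It gave −0.2 points with no link, 0.0 at OR 1.25 per stage step, +1.6 at OR 2, +3.5 at OR 3 and +5.0 at OR 4.

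**4. Type I error under no effect.** Planned model 4.8–5.3%, always adjusting 4.9–5.6%, fixed triggers 4.2–5.2% (Monte Carlo ±0.4).

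**5. How often chance alone would fire the clause.** The data-source table names six variables outside the Aim 1 model: race, education, income, marital status, language preference and insurance status. They are treated here as independent. At N = 400 the standard error of a standardised difference is 2/√400 = 0.10, so the firing probability per variable is q = 2[1 − Φ(t·√400/2)].

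- t = 0.10: q = 31.7%; at least one of six = 1 − (1 − 0.317)^6 = 90%
- t = 0.20: q = 4.6%; at least one of six = 24%
- p < 0.05: 1 − 0.95^6 = 26%

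**6. Effect measure.** With marginal rates fixed at 30% and 45%, the conditional odds ratio given stage runs from 1.95 to 2.31 for stage ORs of 1.47 to 3.15, against the planning value of 1.9.

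**The case against.** The strongest reply is that this is a preference. The plan is valid, its power reproduces, and the only measured benefit rests on an association the documents do not report. That is correct, and it is why the point is put as an improvement. The upper figures are also favourable cases: +7.3 needs SI screening to run from 8% to 60% across stages. If the intervention does nothing in the top stage, a moderate link yields only +0.2 to +1.6 points.

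Second, adjustment is not costless if some participants lack a usable stage. If 5% did (an assumption) and were dropped, 180.5 per arm would give (0.15·√180.5 − 1.342)/0.676 = 0.996, or 84.0% power, a loss of 1.8 points. This calls for a rule on missing stage. It is no reason to omit the variable, since a missing category keeps everyone in the model.

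Third, the 90% firing figure uses a trigger of one standard error, a weak reading of substantial; 24% to 26% is the fairer figure. Insurance status is listed under the administrative database but is also to be ascertained at records review. With five variables the figures are 1 − 0.683^5 = 85% and 1 − 0.954^5 = 21%. Both points stand, but they change how often the clause fires, not the fact that the model is open.

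Fourth, stating a threshold would be a smaller edit, and one may exist elsewhere: this form is a synopsis, and the power text cites a Section 3.3.2 that is not in it. A threshold would remove the ambiguity. It would still leave the covariate set dependent on the data and recover only part of any gain.

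**Conclusion.** The point holds as a recommended improvement, with medium confidence. The Aim 1 model omits a baseline variable planned for all 400 participants before randomization, and it lets others in through an undefined imbalance rule. Pre-specifying stage changes power by about nil if stage is unrelated to screening. It adds about 0 to 4 points for a moderate association (OR per SD 1.47 to 2.0) and about 2 to 7 for a strong one (2.38 to 3.15). All these gains rest on assumed stage categories, distributions and associations. The case for fixing the covariate set in advance needs none of those assumptions. The planned test itself remains unbiased.

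**What to change.** Make both changes before any outcome is tabulated or compared by arm:

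1. Define the Aim 1 primary model as study group, practice, gender, age and baseline overall decision stage. Enter stage as categorical. State its levels, a rule for merging sparse stages on pooled baseline counts (for example, fewer than 20 participants) and a missing category.
2. Remove imbalance-triggered adjustment from the Aim 1 primary model, in both the Aim 1 paragraph and the general analysis text. Keep it as a labelled sensitivity analysis.

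The first change alone leaves the primary model open. Report a covariate-standardised risk difference beside the conditional odds ratio, because the latter will exceed 1.9 if stage is prognostic and the planning rates hold.

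Unblinding cannot serve as the deadline. Only the 12-month records reviewer is described as blinded, and Part F, item 3b provides for interim results without saying whether they are split by arm.

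No change is proposed for Aim 3. Because its strategy is described by reference to Aim 1, the text should say plainly that its own listed covariates stand.

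The cost is plan wording and two or three degrees of freedom, with no new data or participants. If stage is unrelated to screening, the change in power was −0.1 to +0.1 points in the main simulations (Monte Carlo ±0.2).
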